**1.0 LIST OF ABBREVIATIONS**

AE	Adverse Event
C3PR	Cancer Biomedical Informatics Grid
CCTO	Cancer Clinical Trials Office
Co-PI	Co-Investigator
CRA	Clinical Research Assistant
CRF	Case Report Form
CTCAE	Common Terminology Criteria for Adverse Events
DLT	Dose Limiting Toxicity
FDA	Federal Drug Administration
Gy	Gray
GCP	Good Clinical Practice
GRID	Spatially Fractionated Radiation Therapy
IRB	Institutional Review Board
MTD	Maximum Tolerated Dose
NCI	National Cancer Institute
ORRA	Office of Research Regulatory Affairs
PI	Principal Investigator
SAE	Serious Adverse Event
SOP	Standard Operating Procedure
UAMS	University of Arkansas for Medical Sciences

## 2.0 STUDY SCHEMA

## 3.0 STUDY SUMMARY

Title	Phase I clinical trial of GRID therapy in pediatric osteosarcoma of the extremity
Protocol Number	205993
Phase	1
Methodology	Prospective, single-arm “3+3” dose-escalation design
Study Duration	12 months
Study Center(s)	Single center (UAMS)
Objectives	To evaluate the toxicity profile of GRID therapy using dose levels of 10Gy, 15Gy and 20Gy in pediatric osteosarcoma of the extremity.
Number of Subjects Treated	A minimum of 6 and maximum of 12 subjects will be treated.
Diagnosis and Main Inclusion Criteria	Subjects, 5-21 years of age, with a diagnosis of non-metastatic extremity osteosarcoma who have been prescribed GRID radiotherapy by their treating physician
Primary Outcome Measures	Dose-limiting toxicity (DLT), which is defined as a treatment-related AE of Grade 3 or higher, as assessed at either 30 days or 90 days following surgery.
Statistical Methodology	Rule-based evaluation of DLTs to determine the MTD of GRID

## 4.0 BACKGROUND AND RATIONALE

### 4.1 Disease Background

Osteosarcoma response to preoperative chemotherapy is evaluated by histological examination of the resected tumor specimen. Patients who achieve a good histological response to pre-operative chemotherapy, defined as < 10% viable tumor, experience considerably better survival than those who have a poor response ( $\geq 10\%$  viable tumor). Five-year survival for good responders is in the region of 75-80%, compared to 45-55% for poor responders [1, 2]. The percentage of osteosarcoma patients who have good response to pre-operative chemotherapy has ranged in the past from 30% to 55% with recent reports clustering around 45% [1-3].

The likelihood of a patient having a good response to neo-adjuvant chemotherapy is not known until after completion of pre-operative chemotherapy and surgery. The majority of patients achieving a poor response to pre-operative chemotherapy will eventually relapse even with modification in chemotherapy in the adjuvant setting. Radiation therapy is reserved for scenarios wherein complete surgical resection cannot be achieved. Radiotherapy is also recommended for inoperable sites or those with inadequate margins at the time of surgery [15]. Since there is nearly a factor-of-2 difference in survival for good versus poor responders, strategies are needed to predict poor responders to pre-operative chemotherapy so that intensification of treatment can be offered to this group of patients early in their course of treatment.

Radiation therapy can theoretically be used as intensification of therapy prior to surgery for patients with osteosarcoma. However, a 5-week course of conventional radiation therapy in the pre-operative setting may delay not only surgery but the initiation of adjuvant chemotherapy in a group of patients with potentially compromised survival.

A feasible and more tractable possibility is the use of spatially fractionated radiation therapy (GRID) because it is a single-fraction treatment (with doses of 10Gy, 15Gy or 20Gy) that has been shown to have only minor side effects.

Spatially fractionated radiotherapy (GRID) is a technique of irradiation that has been used successfully for the curative or palliative treatment of bulky tumors  $\geq 6$  cm [5-7]. Irradiation is delivered through a specially made grid collimator or by using a multi-leaf collimator (MLC) as a grid field shaper [5, 8-10]. In GRID therapy the target volume does not receive a homogeneous dose of radiation. Only the volume under the open grid areas receives irradiation from the primary beam. Our results [11] have shown that GRID followed by definitive chemoradiation resulted in excellent control of bulky disease (79%) in patients with locally advanced squamous-cell carcinoma of the head and neck. In these patients, acute toxicity profiles were acceptable and were similar to reports of chemotherapy and radiotherapy alone. In addition, no patient has developed a local recurrence in the irradiated GRID volume, but several have developed distant metastatic disease, which is common in this population. Our series also demonstrated that GRID is a feasible and valuable therapeutic option for bulky disease presentation. The therapeutic advantage of GRID therapy has been evaluated. Zwicker [12] et al reported that, for a wide range of tumor radiosensitivities, GRID therapy may have a significant therapeutic advantage over open-field radiotherapy to achieve the same level of tumor-cell kill. Highly radioresistant,

hypoxic cells are often present in bulky untreated tumors, and it is in these cases in which GRID use appears more advantageous.

Based on the above clinical experience, we hypothesize that GRID can be used safely in pediatric patients with osteosarcoma of the extremity, and will show a favorable toxicity profile in this population. However, the toxicity profile of GRID therapy, at any dose level, in pediatric patients is unknown.

Therefore, the purpose of this phase 1 clinical trial is to investigate the toxicity profile of GRID in pediatric osteosarcoma of the extremity.

## 5.0 STUDY OBJECTIVES

### 5.1 Primary Objectives

- 1) **Safety** - To evaluate the toxicity profile of GRID therapy using dose levels of 10Gy, 15Gy and 20Gy in pediatric osteosarcoma of the extremity.

### 5.2 Secondary Objectives

- 1) To determine the maximum tolerated dose (MTD) and/or recommended Phase 2 dose of GRID in patients with pediatric osteosarcoma of the extremity
- 2) To histologically evaluate the extent of tumor necrosis after pre-operative chemotherapy combined with GRID therapy in pediatric osteosarcoma of the extremity patients.

## 6.0 STUDY POPULATION

Research subjects will be recruited from the Radiation Oncology clinic on the UAMS campus. The potential research subject will be identified by the physician during their routine clinic visit. Prior to any research activities, the patient will be approached for participation in the study by their physician, who will discuss the protocol along with the risks and potential benefits of participating in it. A clear statement will be made concerning the voluntary nature of participation and that the decision will have no effect on their remaining care.

We plan to consent up to 15 subjects in order to reach our maximum accrual of 12 subjects. Eligibility waivers are not permitted. Subjects must meet all of the inclusion and exclusion criteria to be enrolled in the study. Study procedures may not begin until a subject is consented.

### 6.1 Inclusion Criteria:

1. History of cytological or histological documentation of non-metastatic extremity osteosarcoma
2. 5 - 21 years of age
3. Subject is eligible for, or has already received, routine chemotherapy for osteosarcoma
4. Subject is eligible for routine surgery for the treatment of non-metastatic extremity osteosarcoma
5. Informed consent is obtained

## 6.2 Exclusion Criteria

1. Women with a positive urine pregnancy test are excluded from this study; women of childbearing potential (defined as those who have not undergone a hysterectomy) must agree to refrain from breast feeding and practice adequate contraception as specified in the informed consent. Adequate contraception consists of oral contraceptive, implantable contraceptives, injectable contraceptives, a double barrier method, or abstinence
2. Unable to comply with study procedures

## 7.0 INVESTIGATIONAL PLAN

### 7.1 Invesigational Plan

Upon consenting to the study, the subject will attend their scheduled routine chemotherapy as prescribed by the treating Pediatric Oncologist (unless subject has already received chemotherapy). This will be followed by radiation treatment as discussed with the Radiation Oncologist. At their radiation treatment visits, the GRID procedure will be implemented. Following the completion of the scheduled radiation treatment, the subject will proceed to routine surgery for osteosarcoma. Post-surgical chemotherapy will be prescribed as per the treating Pediatric Oncologist. Following surgery, the subject will be seen in Radiation Oncology twice for follow-up visits related to their radiation treatment.

### 7.2 Duration of Follow Up

Subject will not be followed once protocol procedures are completed.

### 7.3 Removal of Subject from Study

Subjects will be removed from the study when any of the criteria listed in Section 8.3 apply. The Principal Investigator will be notified, and treating physician will document the reason for study removal and the date the patient was removed in the subject's medical record. The study coordinator will record the reason for removal and date in the Case Report Form (CRF).

## 8.0 STUDY PROCEDURES

### 8.1 Screening/Baseline Procedures

GRID form of radiation therapy is a standard way of delivering radiation therefore no protocol-specific procedures are required.

### 8.2 Study Assessments:

#### 8.2.1 Chemotherapy:

- Subject will receive routine chemotherapy for osteosarcoma (unless subject has already received chemotherapy)

**8.2.2 Radiation Therapy:**

- Subject will receive GRID radiation therapy. GRID radiation therapy is considered a standard radiation therapy method however is not typically used in pediatric osteosarcoma patients. This protocol will evaluate whether or not the use of this therapy will provide benefit to this patient population.

**8.2.3 Surgery:**

- Routine surgery for osteosarcoma

**8.2.4 30 Day Post-Surgery visit (+/- 7 days):**

- Physical exam
- Adverse Event (AE) assessment

**8.2.5 90 day Post-Surgery visit (+/- 7 days):**

- Physical exam
- Adverse Event (AE) assessment

**8.3 Removal of Subjects from Study**

Patients can be taken off the study at any time at their own request, or they may be withdrawn at the discretion of the investigator for safety, behavioral or administrative reasons. The reason(s) for discontinuation will be documented and may include:

- Patient voluntarily withdraws consent from study;
- Patient is unable to comply with protocol requirements;
- Patient experiences toxicity that makes continuation in the protocol unsafe;
- Treating physician judges continuation on the study would not be in the patient's best interest;
- Patient becomes pregnant (pregnancy to be reported along same timelines as a serious adverse event).

**9.0 MEASUREMENT OF EFFECT**

The effects of GRID radiotherapy will be determined by histological examination of the specimen(s) taken during surgery.

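### Section 9.0 credits specimen histology to GRID, but the design can only describe response to chemotherapy and GRID combined

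*Combined protocol and SAP*

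**What the plan says.** Section 9.0 is a single sentence and is the protocol's only statement of how effect is measured: "The effects of GRID radiotherapy will be determined by histological examination of the specimen(s) taken during surgery".

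Section 8.2.2, on radiation therapy, adds: "This protocol will evaluate whether or not the use of this therapy will provide benefit to this patient population". It names no measure of benefit.

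The second objective in Section 5.2 is worded differently: "To histologically evaluate the extent of tumor necrosis after pre-operative chemotherapy combined with GRID therapy".

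The design facts that bear on these sentences are:

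- The methodology in Section 3.0 is "Prospective, single-arm “3+3” dose-escalation design", with 6 to 12 subjects treated.
- Inclusion criterion 3 in Section 6.1 is "Subject is eligible for, or has already received, routine chemotherapy for osteosarcoma". Section 7.1 puts chemotherapy before GRID, then says: "Following the completion of the scheduled radiation treatment, the subject will proceed to routine surgery for osteosarcoma".
- Section 4.1 defines good histological response (under 10% viable tumor) as a response to pre-operative chemotherapy. It says the proportion of patients achieving it "has ranged in the past from 30% to 55% with recent reports clustering around 45" per cent.
- Section 12 has one endpoint, dose-limiting toxicity (DLT), and contains no analysis of histology.

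**The concern.** Section 9.0 assigns to GRID a finding that both treatments produce. Every specimen is taken after chemotherapy and after GRID. The plan has no untreated or chemotherapy-only group, no reference rate, no histology between chemotherapy and GRID, and no analysis that could divide the response between them. The scale itself, percent viable tumor, is the one Section 4.1 already uses for chemotherapy response.

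Sections 9.0 and 5.2 therefore describe different quantities. Section 5.2 names one the trial can observe. Section 9.0 names one it cannot. The benefit sentence in Section 8.2.2 has the same weakness for a separate reason: a single-arm trial of this size with a toxicity endpoint has no means of showing benefit.

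What is at stake is the interpretation of a secondary result. An author following Section 9.0 literally could present an ordinary chemotherapy response as an effect of GRID, and nothing elsewhere in the plan forbids it.

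**Working it through.** **1. The plan's own figure.** The documents give no number for the histology objective. The only related figure is the sample size in Section 12.3. Under Tables 1 to 3 the first cohort has 3 or 6 subjects and the second has 3 or 6, so the total is 3+3 = 6, 3+6 or 6+3 = 9, or 6+6 = 12. The stated range of 6 to 12 reproduces.

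**2. What chemotherapy alone would give.** The inputs are n = 6, 9 or 12 and the good-response rate p = 30%, 45% or 55% from Section 4.1. GRID is assumed to have no effect, and each subject is assumed to give an evaluable specimen. Expected good responders = n × p. The chance of k or more is P(X ≥ k) = Σ C(n,x) pˣ (1−p)ⁿ⁻ˣ over x = k to n. The benchmark of at least half responding is only an illustration; the protocol sets none.

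| n | p | Expected good responders | P(at least half) |
|---|---|---|---|
| 6 | 30% | 1.8 | 25.6% |
| 6 | 45% | 2.7 | 55.8% |
| 6 | 55% | 3.3 | 74.5% |
| 9 | 30% | 2.7 | 9.9% |
| 9 | 45% | 4.05 | 37.9% |
| 9 | 55% | 4.95 | 62.1% |
| 12 | 30% | 3.6 | 11.8% |
| 12 | 45% | 5.4 | 47.3% |
| 12 | 55% | 6.6 | 73.9% |

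With 12 subjects and an inert GRID, 12 × 0.45 = 5.4 good responders are expected, and about 47% of such trials would show at least half responding (74% if the rate is 55%).

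**3. How precise an observed rate would be.** The exact (Clopper-Pearson) 95% limits for x of n are the 2.5% quantile of Beta(x, n−x+1) and the 97.5% quantile of Beta(x+1, n−x).

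| Observed | 95% interval |
|---|---|
| 3/6 | 11.8% to 88.2% |
| 5/12 | 15.2% to 72.3% |
| 6/12 | 21.1% to 78.9% |
| 9/12 | 42.8% to 94.5% |
| 10/12 | 51.6% to 97.9% |

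The interval for 5/12 spans 72.3 − 15.2 = 57.1 percentage points, against 55 − 30 = 25 points for the whole historical range. On the high side, 10 of 12 is the first count whose interval excludes 45%, and even that includes 55%.

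**4. Whether a test against history would help.** The protocol plans none. If one assumed a one-sided 5% test against 45% with 12 subjects, it would need 9 good responders. Its false-positive rate would be 3.6% if the chemotherapy rate is 45%, but 13.4% if it is 55%. Uncertainty about the background rate alone is enough to undermine it.

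**The case against.** The strongest reply is that the plan does not act on the loose sentence. The objective in Section 5.2 names the combination. Section 4.1 closes by giving the trial's purpose as the toxicity profile. Section 12 analyses only DLTs. Wide intervals are also normal for a secondary descriptive measure in Phase 1, and the benchmarks in steps 2 to 4 are not the protocol's. All of this stands, and it limits the point to what may be said about the histology. It does not make Section 9.0 correct.

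Several stronger readings are tempting, and the documents do not support them:

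- *The protocol says histology will show benefit.* Section 8.2.2 does not mention histology and Section 9.0 does not mention benefit. These are two separate sentences.
- *The trial will report a false GRID effect.* No analysis or threshold attributes necrosis to GRID. Misattribution is a risk from the wording and is not certain.
- *The claim will drive the Phase 2 dose.* Section 5.2 does seek a recommended Phase 2 dose, but the rules in Tables 1 to 3 use DLT counts alone.
- *Comparing dose levels would isolate GRID, since chemotherapy is common to all.* Cohorts are sequential, are not randomised and hold 3 or 6 subjects, with at most two levels used. Section 7.1 leaves chemotherapy to the treating oncologist, and it may predate enrolment, so it is not shown to be uniform. Even 0/3 against 3/3 gives a two-sided Fisher p of 2/20 = 0.10.

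One might also argue that the peak-and-valley dose pattern in Section 10.0 allows a contrast within each specimen. That is conceivable, but the protocol plans no such mapping or analysis.

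**Conclusion.** The point holds as a mismatch between what Section 9.0 claims and what the design can show. Chemotherapy and GRID are fully confounded in the specimens, so histology can describe only their combined result. Section 8.2.2 likewise promises an evaluation of benefit that the design cannot deliver.

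The size is set by the protocol's own background rate. With no GRID effect, 3.6 to 6.6 good responders of 12 would be expected across the cited 30% to 55%, and an observed rate near the middle of that range could not be told apart from either end. This rests on the Section 4.1 rates applying to these subjects, independent responses and a full 12 evaluable specimens. Fewer specimens would make the estimate less precise.

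The consequence is confined to interpretation of a secondary objective. The DLT and MTD conclusions do not depend on it. The wording should be corrected, but it does not threaten the trial's main purpose.

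**What to change.** Replace the sentence in Section 9.0 with text such as:

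> Histologic response to the combination of pre-operative chemotherapy and GRID will be reported descriptively, as percent viable tumor and as the number of subjects with <10% viable tumor, with exact 95% confidence intervals, overall and listed by dose level. No effect of GRID alone and no dose-response will be inferred.

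Replace the benefit sentence in Section 8.2.2 with the toxicity aim already stated in Section 5.1. If the 30% to 55% range is shown beside the results, label it as historical context and not as a comparison.

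The cost is two edited sentences and one descriptive table. No subjects are added, and the surgical specimen is already to be examined histologically. The price is that the protocol's stated efficacy claim becomes weaker.

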**10.0 DEVICE INFORMATION**

GRID therapy is to be delivered using a commercially available linear accelerator (Varian Truebeam STX) equipped with a commercially available GRID block (Radiation Product Design GRID block for Varian 64.5cm MLC). The GRID block discretizes the radiation beam from the linear accelerator into multiple smaller beams. The GRID block is a passive beam modifier. That is, it remains static during the delivery of the GRID therapy. The intervening areas between the smaller discretized beams receive much lower doses of radiation as compared to the dose

within the small beam volume. This creates a valley and peak type dose distribution within the GRID target.

## 11.0 ADVERSE EVENTS

### 11.1 Adverse Events Associated with GRID therapy

The potential risks of using a GRID block for radiotherapy delivery are similar to those of radiation therapy using a standard multi-leaf collimator (MLC). The risks are not due to the use of the GRID block itself, but from the actual irradiation as is the case in standard MLC radiotherapy.

Risks and side effects related to GRID therapy include:

Likely:

- Skin reaction (redness)
- Hair loss in the treated area

Less Likely:

- Fatigue
- Reductions in blood counts
- Treatment of large tumors with radiation, chemotherapy and surgery may results in infection or lack of healing which could result in prolonged hospitalization.

Rare:

- Fibrosis (hardening of the tissues)
- Pain in the treated limb
- Swelling
- Fracture of bone
- Bruising of skin
- Neve damage
- Amputation

There exists the potential risk for loss of confidentiality. Measures to protect the confidentiality of study participants will be implemented as described in the Data Handling and Recordkeeping section.

There will be no direct benefits to the study participants; however, knowledge gained from the study could potentially benefits patients in the future.

### 11.2 Adverse Event Monitoring

Adverse event data collection and reporting, which is required as part of every clinical trial, is done to ensure the safety of subjects enrolled in the studies as well as those who will enroll in future studies using similar agents. Adverse events are reported in a routine manner at scheduled times during a trial. Additionally, certain adverse events must be reported in an expedited manner to allow for optimal monitoring of patient safety and care.

All patients experiencing an adverse event will be monitored until the completion of the subject's post-GRID visit:

- the adverse event resolves or the symptoms or signs that constitute the adverse event

return to baseline;

- there is a satisfactory explanation other than the study agent for the changes observed; or
- death.

## 11.3 Definitions

### 11.3.1 Definition of Adverse Event

An adverse event is any untoward medical occurrence in a patient undergoing study assessments and which does not necessarily have a causal relationship with the assessments. An AE can therefore be any unfavorable and unintended sign (including an abnormal laboratory finding), symptom, or disease temporally associated with the study assessments, whether or not related to the assessments.

### 11.3.2 Severity of Adverse Events

Adverse events will be graded according to the NCI Common Terminology Criteria for Adverse Events (CTCAE) version 4.0. The CTCAE v4 is available at <http://ctep.cancer.gov/reporting/ctc.html>

### 11.3.3 Serious Adverse Events

A “serious” adverse event is defined in regulatory terminology as any untoward medical occurrence that:

- Results in death.
  - If death results from (progression of) the disease, the disease should be reported as event (SAE) itself.
- Is life-threatening.
  - The patient was at risk of death at the time of the event; it does not refer to an event that hypothetically might have caused death if it were more severe.
- Requires in-patient hospitalization or prolongation of existing hospitalization for  $\geq 24$  hours.
- Results in persistent or significant disability or incapacity.
- Is a congenital anomaly/birth defect.
- Is an important medical event.

Any event that does not meet the above criteria, but that in the judgment of the investigator jeopardizes the patient, may be considered for reporting as a serious adverse event. The event may require medical or surgical intervention to prevent one of the outcomes listed in the definition of “Serious Adverse Event”.

For example: allergic bronchospasm requiring intensive treatment in an emergency room or at home; convulsions that may not result in hospitalization; development of drug abuse or drug dependency.

